5.4.1 Serious Adverse Events

Investigators (or their delegates) should contact the CI within 24 hours of becoming aware of a suspected SAE.

Participants will be contacted by the principal investigator (PI) and the PI will decide whether a SAE has occurred and act in accordance to Safety Reporting in Non-CTIMP Research Standard Operating Procedures (Appendix 1). The PI will be also asked to provide a categorisation of seriousness and causality. The form should be sent to the CI and a copy kept in the site file.

Investigators should also report SAEs to their own Trust in accordance with local practice.

The Trial Steering Committee/Data and Ethics Monitoring Committee (TSC/DMEC) will monitor all AEs.

The number of SAEs will be reported with proportions and 95% confidence intervals for differences between the groups, where appropriate.

6 Study Objectives

6.1 Primary Objective

To answer the question "Does MOSAIC improve walking ability (measured by the 6MWD) at 3 months compared to usual NHS care in older people with IC?".

6.2 Secondary Objectives

To answer the questions:

- 1) "Does MOSAIC improve:
 - a) activities of daily living and quality of life (QoL) at 3 months and.
 - b) walking ability, activities of daily living and QoL at 6 months compared to usual NHS care in people with IC?"
- 2) Is it feasible to collect the measures required to estimate cost utility in future phase 3 trials in people with IC?
- 3) What are the Minimal Clinically Important Difference (MCID) values for the clinical assessments used for people with IC?

7 Endpoints

7.1 Primary Endpoint

The difference in mean 6MWD at 3 months between the intervention and comparison groups, adjusted for baseline 6MWD and site

7.2 Secondary Endpoints

The difference in mean walking ability at 6 months between the intervention and comparison groups, adjusted for baseline walking ability and site.

The difference in QoL at 6 months between the intervention and comparison groups, adjusted for baseline QoL and site.

The difference in activities of daily living at 6 months between the intervention and comparison groups, adjusted for baseline activities of daily living and site.

The MCIDs for the following measures will be calculated: 6MWD, SR-MWD, WELCH, NEADL, VascuQol-6.

8 Sample Size Considerations

Based on previous work, 192 participants will be required to detect a mean 6MWD difference of 58 metres (standard deviation (SD) =111; α =0.05; 1- β =0.90) accounting for 20% attrition at 3 months follow up.

9 Analysis Sets

The definitions of different analysis populations are shown below:

9.1 ITT Population

The intention to treat population (ITT) comprises all randomised participants, regardless of their compliance with the trial protocol (e.g. eligibility error, post-randomisation withdrawal, and whether the correct trial treatments were received).

9.2 Per-protocol population

A per-protocol population (PP) will also be employed to mirror the ITT population but exclude any patients defined as having a *major protocol deviation*. The planned PP analysis will be applied to the primary outcome only.

Note: A *major protocol deviation* is considered "relevant" if it can be expected that the deviation had a distorting influence on the assessment of the treatment effect on the primary endpoint of the trial or could affect the patient's safety/rights. The items that should be checked are mainly from the inclusion/exclusion criteria as well as other important protocol violations but the final decision regarding important protocol violations and exclusion from the ITT population will be identified by the TSC/DMEC prior to database lock.

9.3 Safety set population

All participants.

10 General Consideration for Data Analyses

10.1 General Methodology

All analyses will not be carried out unless the trial database has been authorised as complete and final, and all protocol deviations have been identified.

The analyses will be performed by the trial statistician and the primary analysis will be reviewed by a second statistician. ITT will be the main strategy of analysis adopted for the primary outcome and the secondary outcomes 1a; 1b and 3. Also, all regression analysis will include the stratification factor, centre, as a covariate.

Continuous data will be summarised in tables using descriptive statistics, including the number of participants, mean, standard deviation, median and range as appropriate. Summaries of continuous characteristics will be based on non-missing observations. For categorical variables, counts and percentage per treatment group will be presented. Percentage for categorical variables will be calculated based on number of patients with non-missing values for the variable. Range checks of the data will be performed to identify anomalous values.

All statistical hypothesis testing will be done using two-sided tests with type I error of 0.05, unless otherwise stated.

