(a) Patients aged ≥50 years with peripheral arterial disease will be identified from existing clinical lists/databases (depending on availability of these at participating sites) at both recruiting sites and Participant Identification Centres and will be invited to participate in the trial using a mailshot approach. Invitation packs will include an information letter including an expression of interest letter and preferred method of contact form, a participant information sheet and a prepaid return envelope. Patients will also be provided with study recruitment personnel contact details for seeking further information. Non-responders will be contacted by telephone by a member of the direct care team approximately 4 weeks later

(b) Eligible patients will be identified and approached by the direct care team during routine appointments.

Written informed consent will be obtained prior to baseline assessment and the participant's Vascular Surgeon, where available and General Practitioner will be informed of their enrolment into the trial.

Sample size: Based on our previous work, 192 participants will be required to detect a mean 6MWD difference of 58 metres (SD=111; α =0.05, 1- β =0.90), accounting for 20% attrition at 3 month follow up.

Justification for recruitment: Participants will be recruited from tertiary centres for vascular surgery (e.g. Guys and St Thomas' NHS Foundation Trust) and District General Hospitals (e.g. Ashford & St Peter's NHS Trust). During our feasibility study, we enrolled 39% of eligible patients approached from two tertiary centres (GSTT and KCH) and estimate that we will recruit ~2 patients/month/site to achieve our target sample in 24 months.

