uptake of other treatment and AEs) and mechanisms of impact (e.g., mediation analysis of psychological processes) will be evaluated. The Brief Illness Perception Questionnaire (Brief IPQ), a measure of individuals' representation of their illness as defined by the Common Sense Model and Theory of Planned Behaviour Questionnaire (TPBQ) which assesses goals and beliefs about walking as treatment for IC will be assessed at each time point. A validated Self-Regulation questionnaire will assess action planning and action control scale (Luszczynska and Schwarzer, 2003; Sniehotta et al., 2005a). To assess adherence to walking goals participants will complete the Exercise Adherence Rating Scale (EARS) at 3 and 6 month follow up assessments

D: Qualitative interviews with participants and physiotherapists

Semi structured interviews lasting 30-60 minutes will be conducted with a purposive sample of up to ~30 participants. Sampling will ensure engagement of trial participants with different age and disease severity. Participants invited to be interviewed will be able to withdraw their consent to being interviewed without withdrawing from the MOSAIC trial or affecting their care. Interviews will last 30-60 minutes, can be conducted via the telephone or face to face either at King's College London, the local hospital or participant's home, based on the participant's preference, and will be arranged at a mutually convenient time. Interviews will be transcribed verbatim, anonymised and analysed thematically. Cross referencing of emerging codes with a second researcher, presenting themes to participants and reporting of deviant findings will be employed to ensure validity of the findings. A sample of ~10 trial Physiotherapists will also be interviewed to explore the experience and implementation of MOSAIC and be given a unique identifier, corresponding personal details will be kept in hard copy only, securely at King's College London.

E: Fidelity assessment

All face-to-face and telephone sessions will be audio recorded with the participants' permission to allow an assessment of fidelity to the protocol. At the end of the study, a random sample of 10% of the recorded sessions per physiotherapist will be reviewed by 2 raters from the research team using standardised checklists to assess treatment fidelity. Any disagreements between raters will be resolved through discussion.

G: MCID assessment

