Motivating Structured walking Activity in Intermittent Claudication (MOSAIC) is a phase II, multi-centre, parallel group, two-arm, randomised, controlled superiority trial with a 1:1 allocation ratio, stratified by recruitment site. Participants will be randomised to receive either usual National Health Service (NHS) care or MOSAIC in addition to usual NHS care.

MOSAIC comprises 2 x 60-minute individual face-to-face consultations (weeks 1 & 2) and 2 x 20-minute follow-up telephone calls (weeks 6 & 12) delivered at a convenient time and location of participant's choice (local NHS Trust or participant's home). All sessions are delivered by a trained Band 6/7 physiotherapist. A checklist outlining the components for each session will be provided to each physiotherapist. All participants randomised to receive MOSAIC will be provided with a pedometer and a patient manual which will include information on intermittent claudication (IC), risk factors, walking guidelines, goal setting, problem solving and action planning worksheets and a walking diary.

Usual care comparison: Participants randomised to the comparison group will continue to receive usual NHS care for IC which typically consists of an initial assessment, drug therapy and simple advice to walk provided by a vascular specialist and delivered in the vascular outpatient clinic. The type and duration of usual NHS care treatment received by both groups will be recorded. The opportunity for between group contamination is low as usual NHS care is not delivered by physiotherapists.

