3.1 Trial Flowchart

4 Method of allocation to groups

Once baseline assessments are complete, the individuals will be randomised to one of the treatment arms. Randomisation will be done in a 1:1 ratio. Randomisation is at the participant level and is performed using an online randomisation system set up by the King's College London Clinical Trials Unit (CTU). Randomisation is stratified by recruitment site with

variable block sizes to ensure that equal numbers of patients are allocated to the two arms within each site. The procedure is as follows: On receipt of the baseline questionnaire, the Trial Co-ordinator electronically submits details of each participant to the CTU. This includes: participant ID number, site, initials and date of birth. The system immediately notifies the chief investigator (CI) and assigned members of the research and clinical teams, as well as recording the randomisation outcome. The Trial Co-ordinator does not receive the randomisation outcome.

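### Clustering by physiotherapist can arise only in the MOSAIC arm and is not allowed for; a prespecified sensitivity analysis of 6MWD should cover it

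*SAP*

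**What the plan says.** SAP section 3 (Study Design) describes MOSAIC as individual consultations and telephone calls and adds: "All sessions are delivered by a trained Band 6/7 physiotherapist". The same section argues that contamination is unlikely because physiotherapists do not deliver usual care. The therapist is therefore a feature of one arm only.

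The primary analysis (SAP 10.6; Protocol 2.4) is a multiple regression of 6MWD with baseline 6MWD and centre as covariates. SAP 10.1 generalises the centre term: "all regression analysis will include the stratification factor, centre, as a covariate". SAP 11.1.3 checks normality and outliers, not independence. Neither document mentions a therapist term, a random effect, a cluster-robust standard error or a sensitivity analysis for any of these.

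The sample size (SAP section 8) says "192 participants will be required to detect a mean 6MWD difference of 58 metres", "accounting for 20% attrition at 3 months follow up". Protocol section 3 gives the same inputs ("SD=111; α =0.05, 1- β =0.90"). No ICC, caseload or design effect appears.

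The number of treating physiotherapists is not stated. The nearest figure is in Protocol 4.4 D: "A sample of ~10 trial Physiotherapists will also be interviewed". Protocol 4.3 and 4.4 E provide for competency assessment, supervision, and fidelity rating of a sample of each physiotherapist's recorded sessions.

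**The concern.** If some physiotherapists achieve more with their patients than others, participants treated by the same one resemble each other more than the regression assumes. The variance of the MOSAIC mean then has a between-therapist part that shrinks with the number of therapists, not with the number of patients. The planned standard error omits it.

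Centre does not stand in for therapist. A centre main effect shifts both arms at a site equally, whereas therapist variation is present in one arm and absent from the other.

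At stake is the interval around the single primary result, which SAP 10.4 makes the main determinant of whether the intervention is judged effective.

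**Working it through.** **Inputs from the documents.** Difference 58 m, SD 111 m, power 0.90, 20% attrition (SAP 8; Protocol 3); two-sided 0.05 (SAP 10.1: "All statistical hypothesis testing will be done using two-sided tests with type I error of 0.05"); allocation (SAP 4: "Randomisation will be done in a 1:1 ratio").

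**Assumptions.** Number of therapists k = 10, with 15 as an alternative; therapist ICC 0.02 to 0.05 on the scale of the analysed outcome; equal caseloads. The documents give none of these. Unequal caseloads would make the effect somewhat larger.

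**1. The plan's own figure.** Per arm, n = 2 × (1.960 + 1.282)² × 111² / 58² = 76.97. In total 153.9, and 153.9 / 0.80 = 192.4. The stated 192 is reproduced, by a formula that assumes independence. Evaluable per arm: 192 × 0.80 / 2 = 76.8, with power 89.9%.

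**2. Design effect in one arm.** With caseload m = 76.8 / k, DE = 1 + (m − 1) × ICC applies to the MOSAIC arm only. The ratio of true to model standard error is r = √((1 + DE) / 2). Coverage of the nominal 95% interval is 2Φ(1.96 / r) − 1.

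| k | m | ICC | DE | r | Coverage |
|---|---|---|---|---|---|
| 10 | 7.68 | 0.01 | 1.067 | 1.017 | 94.6% |
| 10 | 7.68 | 0.02 | 1.134 | 1.033 | 94.2% |
| 10 | 7.68 | 0.05 | 1.334 | 1.080 | 93.0% |
| 15 | 5.12 | 0.02 | 1.082 | 1.020 | 94.5% |
| 15 | 5.12 | 0.05 | 1.206 | 1.050 | 93.8% |

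At ICC 0 nothing changes.

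**3. In metres, with SD 111.** The model standard error is 111 × √(2 / 76.8) = 17.9 m, a half-width of 1.96 × 17.9 = 35.1 m. With k = 10 the true values are 18.5 m and 36.3 m (ICC 0.02), or 19.4 m and 37.9 m (ICC 0.05).

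**4. Does the centre term help?** The planned model was simulated with centre fixed effects and 10 therapists, with the true mean effect set to zero but therapists differing. In the runs whose layout was specified, there were four sites, as the recruitment rate in Protocol 3 implies (192 / (2 × 24) = 4), with therapists nested in site. Two sets of runs gave these rates for the interval missing the true value: 4.8% and 5.0% at ICC 0; 5.8% and 5.9% at ICC 0.02; 6.4% and 7.6% at ICC 0.05. These lie close to the formula's 5.8% and 7.0%, so adjusting for centre does not remove the excess.

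**5. Power.** With a correct standard error and SD 111 taken as it stands, power for k = 10 is Φ(58 / SE − 1.96) = 88.0% (ICC 0.02) or 85.0% (ICC 0.05). The planned model also adjusts for baseline, and the sample size takes no stated credit for that. If 111 is the unadjusted SD and ρ is the correlation of baseline with 3-month 6MWD, the SD becomes 111 × √(1 − ρ²):
- ρ = 0.3: 90.8% and 88.1%
- ρ = 0.5: 95.2% and 93.3%

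If baseline adjustment leaves the therapist variance at its unadjusted size, these become 90.6% and 87.7%, then 94.8% and 92.2%. The planned power is restored at ρ = √(1 − 2 / (1 + DE)) = 0.25 (ICC 0.02) or 0.38 (ICC 0.05). The documents give neither ρ nor the type of SD.

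**6. How well could therapist variance be estimated?** With 10 equal caseloads the estimate is zero when the between-therapist F ratio falls below 1. That probability is P(F with 9 and 66.8 df < 1 / (1 + m × ICC / (1 − ICC))), with bounds 0.865 and 0.712. It is about 44% at ICC 0.02 and 30% at ICC 0.05.

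**The case against.** **The ICC may be close to zero.** Training to competency and continuing supervision are there to make delivery uniform, and fidelity checks do not prove that outcomes differ by therapist. This stands: the interval is too narrow only on the condition that the ICC exceeds zero, and at 0.01 to 0.02 with 10 therapists the effect is small.

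**Type I error.** A reader might infer that the false-positive rate of the primary test is above 5%. The documents do not support that as a general statement. If MOSAIC does nothing for anyone, therapists cannot differ through it and the test keeps its size. Inflation needs an average effect of zero made up of therapists who help and therapists who harm. The sound claim is about coverage when MOSAIC has an effect that varies by therapist.

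**Power.** A reader might also infer that the trial falls short of 90%. Step 5 shows why this is not established: a modest baseline correlation would make up the loss. Baseline adjustment does not, however, correct the understated standard error.

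**Very few therapists.** Calculations with four or six therapists give much larger effects. The only figure in the documents is an interview sample of about 10, which points to 10 or more, so those cases should not be used to size the problem.

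**Inference target.** One may regard the result as applying to these physiotherapists alone, in which case no therapist variance is needed. That is defensible for a phase II trial, but the plan does not say so, and it looks ahead to phase 3.

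**Replacing the primary model.** Step 6 argues against making the therapist model the sole primary analysis, since it would often collapse to no therapist effect. This stands, and the fix respects it.

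**Conclusion.** The omission is real and its likely size is modest. Therapists deliver treatment in one arm only, the primary regression and the sample size treat participants as independent, and centre adjustment does not repair this. If the therapist ICC exceeds zero, the interval is too narrow. With about 10 therapists and an ICC of 0.02 to 0.05, the true standard error is about 3% to 8% larger than reported and coverage is about 94% to 93%; with 15 therapists the excess is about 2% to 5%. All of these rest on an assumed ICC and number of therapists.

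The sample size contains no margin for clustering, but neither a shortfall below 90% power nor a general breach of the 5% error rate is shown. This is a worthwhile, low-cost addition to the SAP, not a reason to replace the primary analysis.

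**What to change.** Keep the planned ANCOVA as the primary analysis. Add to the SAP, before database lock:

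- **Sensitivity analysis of 3-month 6MWD.** A mixed model with a random physiotherapist effect in the MOSAIC arm only, arm-specific residual variance, baseline 6MWD and centre as fixed covariates, and a small-sample degrees-of-freedom correction.
- **Fallback, fixed in advance.** If the model does not converge or the therapist variance is estimated as zero, report the ANCOVA with a small-sample-corrected cluster-robust standard error by therapist, each usual-care participant being a cluster of one.
- **Data.** Carry the treating physiotherapist's identifier into the analysis dataset. Fidelity sampling by physiotherapist implies that it is known, but the case report form contents in Protocol section 9 do not list it. State how MOSAIC participants seen by more than one physiotherapist, or by none, are classified.
- **Reporting.** Give the number of therapists, their caseloads, and the ICC with its interval. State the ICC assumed at the planning stage.

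The cost is one extra model in the planned software and some SAP wording, with no extra participants. The drawbacks are a possibly wider interval and an imprecise ICC from few therapists. The change does not add power.

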10.2 Loss to follow up and Missing Data

At 3 and 6 month follow up attrition will be minimised via standardised telephone, text and email reminders to participants:

• First reminder: (+7 days) email reminder (if email provided) or text reminder (if mobile provided) with the option to request a link to online questionnaire or a new or additional paper copy.

• Second reminder: (+14 days) email reminder (if provided and not already contacted via email), or second text-reminder (if mobile provided).

• Third reminder: (+21 days) telephone call to request completion of minimum data set by telephone (< 10 minutes duration).

10.3 Interim Analysis and Data Monitoring

No interim analysis for data monitoring purposes is planned. No adjustment for interim analyses is necessary for data monitoring.

10.4 Multiple Comparison/multiplicity adjustments

Adjustments for multiple comparisons will not be made in this trial since there is a single primary outcome which will be used as the main determinant of effectiveness of the intervention.

10.5 Sociodemographic and Clinical Descriptive Characteristics

Summary statistics of the sociodemographic and clinical characteristics collected by selfreport or by the outcome assessor at baseline will be reported.

10.5.1 Exploratory analyses

Exploratory analyses will be performed to provide an overview of the data and the distributions of each of the continuous variables will be produced. For categorical variables contingency tables will be produced and bar charts, where appropriate.

10.6 Primary Analysis

The analysis will be conducted using the ITT population. The primary outcome will be analysed using multiple regression with the baseline 6MWD value and the stratification factor, centre, included as covariates. Results will be reported as the mean difference in 6MWD between the intervention and control group with a 95% confidence interval.

11 Secondary analysis

The secondary endpoints QoL and activities of daily living, will at both 3 and 6 months be analysed respectively using multiple regression with the baseline value and the stratification factor, centre, included as covariates. Results will be reported as the mean difference in the relevant secondary endpoint between the intervention and control groups with a 95% confidence interval. Other continuous outcomes will be similarly analysed.

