4.4 Follow up Procedures

None of the assessments listed below are part of usual care for this population.

A: Clinical assessments

Baseline and post-intervention (3-month) follow-up measures will be collected at either King's College London or the local hospital (subject to availability and patient preference). Participants who are unable or refuse to attend, and therefore cannot complete the primary outcome, will be invited to complete secondary outcomes at home either electronically using a computer or phone or via a standard postal pack with pre-stamped return envelope. At 6-months all self-reported measures will be collected from participants either electronically or via a standard postal pack with pre-stamped return envelope. Attrition will be minimised via standardised telephone, text and email reminders to participants.

- First reminder: (+7 days) email reminder (if email provided) or text reminder (if mobile provided) with the option to request a link to online questionnaire or a new or additional paper copy.
- Second reminder: (+14 days) email reminder (if provided and not already contacted via email), or second text-reminder (if mobile provided)
- Third reminder: (+21 days) telephone call to request completion of minimum data set by telephone (< 10 minutes duration).

Baseline visit:

Sociodemographic & clinical characteristics including age, gender, smoking history and comorbidities will be collected at baseline by self-report and standard measures of body mass index and Ankle-Brachial Pressure Index obtained. The SDCQ will also be repeated to describe current IC symptoms.

Primary outcome: 6 Minute Walking Distance (6MWD in metres) is measured during a selfpaced, standardised 6 Minute Walk Test (6MWT) conducted around a level, 100-foot circuit (Montgomery et al., 1998; American Thoracic Society, 2002). During the 6MWT, maximal walking ability (time (seconds) walked before resting) and pain free walking ability (time (seconds) walked before reported pain onset) will be measured. Pain intensity will also be measured before and after the walking test using the Claudication Pain Scale. The walk test is completed twice, with the results from the best test used for analysis.

Secondary outcomes:

Self-reported Maximum Walking Distance (SR-MWD) is measured by one global item: "What is the maximum distance (in metres) you can walk at your usual pace on a flat surface before leg pain forces you to stop?"

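### The primary analysis is labelled ITT, but its regression can use only participants with a 3-month 6MWD, and the SAP gives no method for the rest

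*SAP*

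**What the plan says.** SAP 10.6 assigns the primary analysis to the ITT population and gives one model: "The primary outcome will be analysed using multiple regression with the baseline 6MWD value and the stratification factor, centre, included as covariates". According to SAP 9.1, the ITT population "comprises all randomised participants, regardless of their compliance with the trial protocol". Protocol 2.4 describes the same analysis.

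6MWD is scheduled at baseline and 3 months only, because the 6-month follow-up is by self-report. For the 3-month visit, Protocol 4.4 adds: "Participants who are unable or refuse to attend, and therefore cannot complete the primary outcome, will be invited to complete secondary outcomes at home". The 3-month secondary outcomes include SR-MWD, WELCH, NEADL, VascuQoL-6 and IPAQ.

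SAP 8 plans for the loss: "192 participants will be required to detect a mean 6MWD difference of 58 metres", "accounting for 20% attrition at 3 months follow up".

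SAP 10.2 has missing data in its title but holds only the reminder schedule, ending in a telephone call for a minimum data set. Neither document gives an imputation rule, a missing-data assumption, a missing-data sensitivity analysis, or a statement that the analysis is of complete cases. The one section headed as a sensitivity analysis (SAP 11.1.2) concerns the MCID. The per-protocol set (SAP 9.2) removes major deviators and does not deal with absent outcomes.

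**The concern.** A participant with no 3-month walk test has no outcome value, so an ordinary regression drops that person. The label says all randomised, but the model analyses those observed, and no text connects the two.

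The walk test requires attendance, and some people who cannot attend may be absent because they walk poorly. Participants also know whether they received physiotherapist sessions and a pedometer, so reasons for staying away could differ by arm. If they do, and baseline 6MWD and centre do not account for the difference, the estimated effect is distorted.

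The trial plans to ask these same people about their walking at 3 months, yet the SAP makes no use of the answers in the primary analysis. With no rule written down, the handling of missing 6MWD would be settled after the data are seen.

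**Working it through.** **Inputs from the documents.** Difference 58 m, "standard deviation (SD) =111", power 0.90 and 20% attrition (SAP 8); two-sided 0.05 (SAP 10.1); 1:1 allocation (SAP 4). The feasibility study had 92% retention and 86% completing all measures, n=24 (Protocol 1).

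**1. The plan's own figure.** n per arm = 2 × [111 × (1.960 + 1.282) / 58]² = 76.97, or 153.94 in total. Allowing for attrition, 153.94 / 0.8 = 192.4. The stated 192 is reproduced.

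**2. Who enters the regression.** 192 × 0.8 = 153.6, about 154 (76.8 per arm). About 38 randomised participants do not enter.

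**3. Precision.** SE = 111 × √(2/76.8) = 17.91 m, 95% half-width 1.96 × 17.91 = 35.1 m, and power Φ(58/17.91 − 1.96) = 89.9%. With all 192 measured, power would be 95.2%. The allowance therefore protects the planned power but does nothing about bias.

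**4. Size of a possible shift.** Let π be the fraction missing and d the average shortfall of the missing participants against the model's prediction, in each arm. The MOSAIC effect is overstated by π_MOSAIC × d_MOSAIC − π_usual × d_usual. Equal mechanisms cancel. With a shortfall in the MOSAIC arm only:

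| Fraction missing | d = 20 m | d = 50 m | d = 111 m |
|---|---|---|---|
| 8% (from 92% retention) | 1.6 m | 4.0 m | 8.9 m |
| 14% (from 86% completion) | 2.8 m | 7.0 m | 15.5 m |
| 20% (planned allowance) | 4.0 m | 10.0 m | 22.2 m |

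The same shortfall in usual care only gives the same sizes with the opposite sign. The values of d are assumptions.

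**5. Tipping point.** From an observed 58 m at 20% missing in one arm, significance is lost when 58 − 0.2d = 35.1, so d is about 114 m. This holds the SE at 17.91 m and uses the unadjusted SD. Adjustment for baseline would narrow the interval and move the point further out.

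**6. Simulation.** Assumed: n=192, SD 111, correlation of baseline with 3-month 6MWD 0.7, correlation of a 3-month questionnaire with 6MWD 0.4 or 0.6, 20% missing per arm, no centre effect, and regression imputation by arm as a stand-in for the multiple-imputation point estimate. There were 600 replicates per scenario, at true effects of 0 and 58 m. Bias is measured against the analysis of full data.

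| Mechanism | Complete cases | Imputed, all non-attenders reply | Imputed, 50% reply |
|---|---|---|---|
| Low questionnaire score raises missingness in both arms | within 0.5 m of 0 | within 0.5 m of 0 | within 0.5 m of 0 |
| Same in MOSAIC only, correlation 0.4 | about +5 m | about 0 m | about +2.6 m |
| Same in MOSAIC only, correlation 0.6 | about +8 m | about 0 m | about +4 m |

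The full-reply column is a favourable case, because the score that drives missingness is also the score used to impute.

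**The case against.** The strongest reply is that nothing here shows the estimate to be biased. Difficulty in attending because of poor walking applies to both arms, the model already conditions on baseline 6MWD and centre, and the check finds complete cases essentially unbiased when the mechanism is common. An arm-specific mechanism is a supposition, and if usual-care participants who did badly stayed away, the effect would be understated. The 20% is an openly stated allowance, and the feasibility study points to less, though with only 24 people. Even a 10 m shift is small beside a 35.1 m half-width. All of this stands, and it limits the point to an unaddressed risk of modest size.

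It is also true that non-attenders are only invited to reply. No response rate is given, and part of the attrition may return nothing. Where the protocol defines the telephone minimum data set (for 6 months), it contains SR-MWD, IPAQ and VascuQoL-6 but not WELCH. A reader might infer that walking questionnaires will exist for most people without a walk test; the documents do not support that.

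A reader might also infer that the questionnaire regressions in SAP 11 suffer the same loss. They need not: the 3-month questionnaires can be completed at home and the 6-month ones are all remote. Nor do the documents show a need to replace those regressions with a single mixed model, which would be a modelling preference.

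What the reply does not answer is the missing rule. The SAP defines a population of all randomised, specifies a model that cannot include them all, and does not say what is assumed about the rest.

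**Conclusion.** The omission is certain from the text: no missing-data method, no stated assumption, and an ITT label that the specified regression cannot meet for anyone without a 3-month 6MWD, about 38 of 192 at the planned attrition. It should be corrected before analysis.

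The consequence is conditional. Bias needs missingness that relates to outcome beyond baseline 6MWD and centre and that differs between arms. If it occurs in one arm only, the shift is the fraction missing times d: 4 to 10 m for d of 20 to 50 m at 20% missing, and 1.6 to 4 m at 8%. The mechanism, the values of d, the correlations and the 50% reply rate are assumptions.

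Two stronger readings fail. The sample size is not wrong, since 192 already carries the attrition. And a result at the design effect would not easily be overturned, since that takes a departure of about 114 m among one arm's missing participants.

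**What to change.** In SAP 10.2 and 10.6:

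- State the missing-at-random assumption, and describe the plain regression as an analysis of participants with an observed 3-month 6MWD.
- Pre-specify the same ANCOVA on data multiply imputed separately by arm, using baseline 6MWD, centre, and baseline and 3-month SR-MWD, VascuQoL-6, IPAQ and (where returned) WELCH. The 3-month questionnaires are what add information, because the regression already uses baseline 6MWD and centre. Report the result together with the complete-case result, and say in advance which of the two carries the conclusion.
- Add a delta-adjusted sensitivity analysis over all randomised participants, with shifts applied to each arm separately and extended to the tipping point. A range stopping at 60 m would move the estimate by at most 0.2 × 60 = 12 m at 20% missing and would not reach it.

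The cost is SAP wording and some extra Stata programming. There are no new data and no change to the sample size. The limitation is that the gain depends on how many non-attenders return questionnaires: in the simulation, about half the bias was removed at 50% return.
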